MTAC Clinical Trial protocol

June 2008

Version 2

West London Renal and Transplant Unit

EudraCT Number 2008-001009-41

REC reference number 08/H072090

Full trial name -Mycophenylate mofetil and tacrolimus vs tacrolimus alone for the treatment of idiopathic membranous glomerulonephritis

Abbreviated trial name MTAC

Summary

Membranous nephropathy is a common cause of nephrotic syndrome in adults. It is difficult to treat and if persistent leads to end stage renal failure in a significant number of patients. It is currently treated in this institution with tacrolimus monotherapy. This is effective in the majority of patients in reducing proteinuria but the remissions are often partial and patients tend to relapse when the tacrolimus treatment is stopped. We propose to use mycophenylate mofetil in combination with tacrolimus with the aim of obtaining a more complete initial response to treatment, a decreased rate of relapse on withdrawal of therapy and less progression of renal failure.

Principal Investigators

Drs [name] [name] and [name]

Renal Unit

[name]

Hammersmith Hospital

[name]

[name]

Sponsorship provided by Imperial College Healthcare NHS Trust ref no GRIM1001

Contents

	Page number
Title Page	1
Contents	2
1. Background	3
1.1 Membranous Glomerulonephritis	3
1.2 Mycophenylate Mofetil in membranous glomerulonephritis	3
2. Aims of MTAC	4
3. Hypothesis	4
4. Trial Design	4
4.1 Eligibility	5
4.2 Trial Protocol	5
4.3 Evaluations	6
4.4 Withdrawal and treatment failure	6

1.1 Membranous Glomerulonephritis

Idiopathic membranous nephropathy is the most common cause of nephrotic syndrome in Caucasian adults and up to 40% of patients eventually develop end stage renal failure (1). Historically used treatment regimes include high dose prednisolone, chlorambucil, and cyclophosphamide. Although these are effective in some patients there are significant side effects from the treatment hence the need to seek alternative immunosuppressive regimes. Cyclosporin is a well tolerated immunosuppressive agent used widely in transplantation, this has been shown to be effective in membranous nephropathy but there is a high incidence of relapse on withdrawal of therapy and long term risks of a decline in renal function due to nephrotoxicity (2). Tacrolimus is an alternative calcineurin inhibitor with less nephrotoxicity which has been shown to be very effective in the treatment of membranous nephropathy but there remains a high risk of relapse on withdrawal of therapy (3). Tacrolimus alone is the current standard therapy in this institution.

1.2 Mycophenylate Mofetil in membranous glomerulonephritis

Experimental models of membranous glomerulonephritis show that damage to the glomerular basement membrane by the deposition of immunoglobulin results in proteinuria (4). Mycophenylate mofetil (MMF) is an immuno-suppressive agent which inhibits de novo purine nucleotide synthesis and the depletion of guanosine triphosphate (GTP) in lymphocytes and monocytes. Thus it selectively suppresses T and B lymphocyte proliferation and antibody formation, and is therefore likely to be effective in modifying this process. It has been used widely in other autoimmune diseases and has low toxicity (5). It has been shown to be effective in the treatment of membranous nephropathy when used in combination with high dose steroids (6,7,8). However there are significant side effects from the steroids and we wish to avoid these in our patients. MMF has been used in combination with tacrolimus in

transplantation, and this regime is better tolerated than those containing even low dose steroids (9). We hope that the addition of MMF to tacrolimus will result in improved remission rates from proteinuria for patients, improved preservation of renal function, will be well tolerated and will allow the eventual withdrawal of immunosuppressive agents without relapse thus avoiding the long term toxicity of ongoing treatment with these agents.

2. Aims of MTAC

To investigate if combining mycophenylate mofetil (MMF) with tacrolimus has a beneficial effect over tacrolimus therapy alone in the treatment of membranous glomerulonephritis. Tacrolimus alone is often effective in producing remission from heavy proteinuria but patients often relapse when the tacrolimus is withdrawn. We wish to investigate whether the addition of MMF will allow the subsequent withdrawal of tacrolimus without precipitating relapse. We will also study whether the addition of MMF to standard therapy with tacrolimus will be more effective in obtaining remission of proteinuria and preserving renal function

3.Hypothesis

When MMF is added to tacrolimus in the treatment of membranous glomerulonephritis, it is likely to improve the initial response to treatment and reduce the risk of relapse on stopping therapy.

4. Trial Design

This will be a randomized controlled trial in a single centre of tacrolimus alone vs tacrolimus and MMF therapy in 32 patients with heavy proteinuria secondary to

idiopathic membranous glomerulonephritis diagnosed by renal biopsy. We aim to recruit 32 patients 16 to each arm of the trial.

4.1 Eligibility

a) Inclusion criteria (requires all)

1. Idiopathic membranous glomerulonephritis on renal biopsy
2. Proteinuria – protein/creatinine ratio (PCR) >100units with hypoalbuminaemia or PCR >300 units with normal serum albumin despite 3 months treatment with maximum tolerated doses of ace inhibitors and angiotensin 2 antagonists; (or shorter if life threatening complications of nephrotic syndrome require institution of immediate immunosuppression.)
3. Male or female patients aged 18 to 80 years.

b) Exclusion Criteria

- 1 Hepatitis B hepatitis C or HIV positive
- 2 Malignancy (all patients must have a CT chest abdomen and pelvis and other investigations if clinically indicated).
3. Untreated infection
4. Females who are pregnant, breast feeding, or at risk of pregnancy and not using a medically acceptable form of contraception.
5. Any condition judged by the investigator that would cause the study to be detrimental to the patient.

4.2 Trial Protocol

The research will be conducted via the glomerulonephritis clinic at Hammersmith Hospital. All patients with significant proteinuria secondary to membranous glomerulonephritis on renal biopsy will be considered for the trial. Patients will be screened for hepatitis B, C and HIV, and undergo CT chest, abdomen and pelvis to exclude viral and malignant causes for their membranous nephropathy (these are the

current standard investigations in all patients with membranous nephropathy.) All patients will be initially treated with maximum tolerated doses of ace inhibitors and angiotensin two antagonists for at least 3 months as is standard current treatment. Patients who remain significantly proteinuric (PCR>100units with hypoalbuminaemia or PCR >300 units with normal serum albumin) despite treatment with maximum tolerated doses of ACE inhibitors and angiotensin two antagonists will be randomised to receive tacrolimus monotherapy or tacrolimus in combination with mycophenylate mofetil therapy. The initial dose of tacrolimus will be 2mg twice a day and this would be titrated to achieve levels of 5-12 ng/ml. The initial dose of mycophenylate mofetil would be 500mg twice a day, and this would be titrated to achieve mycophenolic acid levels of 1.5-3.0 mg/L. Patients with a previous history of tuberculosis, or deemed at high risk due to Asian origin will receive isoniazid 150mg once a day and pyridoxine 50mg once a week.

Treatment will be initially for 1 year. Remission of proteinuria will be defined as complete if urinary PCR <30 units, and partial if urine PCR decreases by >50% but is still above 30 units. Patients not obtaining complete or partial remission after 1 year will be withdrawn from the trial and alternative therapies considered. When patients have been in remission for 12 months on treatment the tacrolimus will be withdrawn over 6 months. Those on MMF and tacrolimus will then have their MMF stopped prior to tacrolimus withdrawal over 6 months. Patients will be offered a renal biopsy prior to withdrawal of therapy. This will help predict relapse and show any evidence of tacrolimus toxicity which may help guide subsequent therapy in the case of relapse. Continuation in the trial is not dependent on undergoing renal biopsy. Patients will be followed for at least 3 years. Patients may withdraw from the trial at any point without any compromise to their clinical care.

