4.3 Evaluations

The patients will initially be seen weekly until stable and then monthly until remission is achieved. They will then be reviewed 2-3 monthly for the rest of the trial depending on clinical need. Prior to entry all patients will have blood sent for hepatitis B

hepatitis C and HIV and have a CT scan of chest abdomen and pelvis to exclude malignancy.

At each clinic visit blood samples will be sent for full blood count, biochemical profile, drug level monitoring and selective proteinuria. Urine samples will be sent for PCR and selective proteinuria.

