4.5 End points

a) Primary Endpoints

Efficacy of MMF in preventing relapse of nephrotic syndrome on withdrawal of tacrolimus therapy. This will be initially measured at 6 months post withdrawal of tacrolimus therapy.

b) Secondary end points

The time to obtaining remission from proteinuria

The degree of remission of proteinuria obtained (complete or partial)

The rate of decline of renal function measured by the MDRD equation for glomerular filtration rate

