4.7 Duration

5 years, with 24 months recruitment and 36 months follow up. Primary end points will be analysed when patients obtaining remission for 1 year have stopped tacrolimus therapy for 6 months. Secondary end point analysis of response to treatment will occur when patients have been on treatment for 12 months.

5. Adverse Events and Data Monitoring

It is anticipated that the treatment will be well tolerated as this regime has been extensively used in renal transplant recipients. All adverse events will be actively sort and recorded in the patients' notes. The data and progress of the trial will be reported to and monitored by the West London Renal and Transplant Glomerulonephritis Research Group at Hammersmith Hospital , on a monthly basis (appendix 2).

All Serious Adverse Events (SAE) and Suspected Unexpected Serious Adverse Drug Reactions (SUSADR) will be reported within 24 hours to the committee chairman [name] and to the sponsor, [name], i.e all events irrespective of their relation to study medications, that are either life threatening, result in hospitalization, result in death, result in persistent or significant disability or incapacity . The sponsor will report any such SAE or SUSAR to the regulatory authority in accordance with the European Directive 2001/20/EC.

6. Internal and External Review

The trial has been extensively reviewed, modified and approved by the West London Renal and Transplant Glomerulonephritis Research Group at Hammersmith Hospital. It has been externally reviewed and approved by [name], Professor of Medicine, The Rayne Institute, University College London [name].

Appendix 1
MTAC Trial Overview

Entry
(eligibility criteria)

Randomisation
(16 patients per limb)

Tacrolimus 2mg bd
adjusted to obtain levels of 5-11

MMF 500mg bd
adjusted to obtain levels of 1.5-3.0
and Tacrolimus 2mg bd adjusted to
obtain levels of 5-12ng/L

(treatment for minimum 12months maximum 24 months)

Patients in remission for 12 months

Withdrawal of tacrolimus over 6 months Withdrawal of tacrolimus over 6 months
Stop MMF

Monitor patients for relapse of nephrotic syndrome

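### Remission is defined without a reference PCR or a confirming value, so one low reading among roughly 12 to 18 tests can date the secondary endpoint of time to remission

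*Combined protocol and SAP*

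**What the plan says.** Section 4.2 gives the rule: "Remission of proteinuria will be defined as complete if urinary PCR <30 units, and partial if urine PCR decreases by >50" per cent. The partial category in full is "partial if urine PCR decreases by >50% but is still above 30 units". No section says whether the fall is measured from a screening value, the value at randomisation or an average, and none asks for a repeat.

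Section 4.3 sets how often the rule can be met: "The patients will initially be seen weekly until stable and then monthly until remission is achieved". At each of these visits, "Urine samples will be sent for PCR and selective proteinuria". The length of the weekly phase is not fixed.

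The window is one year: "Patients not obtaining complete or partial remission after 1 year will be withdrawn from the trial" (section 4.2).

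Section 4.5 lists as its first secondary endpoint "The time to obtaining remission from proteinuria", followed by the degree of remission. Section 4.7 adds: "Secondary end point analysis of response to treatment will occur when patients have been on treatment for 12 months".

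The only durability condition is in section 4.2: "When patients have been in remission for 12 months on treatment the tacrolimus will be withdrawn over 6 months". It governs when tacrolimus is withdrawn. It does not define when remission starts.

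**The concern.** Time to remission is how the trial examines the first half of its hypothesis (section 3), a better initial response with MMF. An endpoint dated at the first crossing of a threshold is sensitive to noise when the threshold is tested many times. A patient whose PCR varies around a modest fall has many chances to produce one value more than 50% below a reference value, which may itself have been a chance high.

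Such false remissions occur in both arms, but most often in the arm with fewer true responders. The two curves then move together, and with 16 patients per arm a few misclassified patients matter. Because the reference value is not named, two assessors could also date the same patient differently.

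**Working it through.** **The plan's own figure.** The plan gives no figure for remission. Its one calculation (section 4.6) concerns relapse and reproduces by Freedman's log-rank method:
- HR = ln 0.95 / ln 0.50 = 0.074.
- Events = (1.645 + 0.842)² × (1.074/0.926)² ≈ 8.32.
- N = 2 × 8.32 / (2 − 0.50 − 0.95) = 30.2, and 30.2/0.99 = 30.5, which rounds up to 16 per arm, or 32.

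The remission rule is not an input, so 32 is unaffected.

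**Inputs.** From the documents: the 50% threshold, weekly then monthly testing, and the one-year window. Assumed:
- 4 weekly and 11 monthly tests, 15 in all. Weekly phases of 0 and 8 weeks give 12 and 18.
- Log-normal PCR with independent error between visits.
- One reference value with the same error.
- Within-patient SD of log PCR, *s*, of 0.1 to 0.3. The documents give none.

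**One test.** For a true fall *f*, the chance that a single later value is more than 50% below the reference is Φ( ln(0.5/(1−f)) / (s√2) ). With s = 0.2 and f = 0.3: ln(0.5/0.7) = −0.336, divided by 0.283 gives −1.19, so the chance is 12%.

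**Any of k tests.** Given a reference error *b* ~ N(0, s²), each test qualifies with probability p(b) = Φ( (ln(0.5/(1−f)) + b)/s ). The chance of at least one qualifying value is the average of 1 − (1 − p(b))^k over *b*. For two consecutive values, the same p(b) is carried through a run-of-two recursion. Results for k = 15, true fall 20% / 30% / 40%:

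| Scoring | s = 0.1 | s = 0.2 | s = 0.3 |
|---|---|---|---|
| One test at year end | <1 / 1 / 10% | 5 / 12 / 26% | 13 / 21 / 33% |
| Any single value | <1 / 8 / 47% | 29 / 51 / 76% | 56 / 70 / 84% |
| Two consecutive values | <1 / 1 / 16% | 7 / 19 / 43% | 23 / 36 / 54% |

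Comparing the first two rows shows that repeated testing drives much of the excess. The length of the weekly phase matters little: at s = 0.2, going from 12 to 18 tests moves the single-value figures over 26.3–31.7%, 47.8–54.5% and 73.2–78.8%.

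**Gradual fall.** The table assumes the full fall from the first visit. If it develops over six months, simulation of the single-value rule gives about 23–49%, 41–62% and 66–76% for s = 0.2 to 0.3.

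**Blunting.** Simulated trials had 16 per arm and true responders (70% fall) in 50% versus 90% of patients. All other patients had a true fall of 20–40%, and the full fall was reached between months 3 and 9. The test was a two-sided 0.05 log-rank. CV 20% and 30% correspond to s of about 0.20 and 0.29.

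| Scoring | Remitters, CV 20% | Power | Remitters, CV 30% | Power |
|---|---|---|---|---|
| True remission times | 50 vs 90% | 66% | 50 vs 90% | 66% |
| Any single value | 70 vs 94% | 45% | 80 vs 96% | 25% |
| Two consecutive values | 57 vs 91% | 58% | 62 vs 90% | 41% |

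At s = 0.1, with a six-month fall and the mean of two values as reference, confirmation cost no power (about 65% single, 66% confirmed).

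**The case against.** **The plan does not say that one value is enough.** A reader might infer a stated single-value rule measured against a single baseline. The text only permits this by silence, and a clinic might in practice repeat a doubtful result. This stands, so the defect is an unspecified definition.

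**The size rests on an undocumented figure.** This also stands. At s = 0.1 only falls near 40% are affected. The number of patients with a true fall of 20–40% is unknown, and the protocol summary says tacrolimus reduces proteinuria in most patients. The power example gives every non-responder such a fall, which favours the concern. Errors between weekly visits may also be correlated.

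**The remission share need not be inflated.** A reader might infer that the proportion in remission is overstated as well. Sections 4.4 and 4.7 can be read as status at one year, for which the one-test row applies. The share is affected by repeated testing only if it is scored as ever reached.

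**The primary endpoint has its own safeguard.** A reader might infer that noise-driven remitters pass freely into tacrolimus withdrawal. Twelve months in remission is required first. If every one of five further visits had to qualify, only 0.1–4% of patients with a true 20–40% fall would pass at CV 20%. The documents do not say how those 12 months are judged, so the protection is likely but not fixed.

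**Review frequency is a separate matter.** Section 4.3 leaves later review to clinical need, and the scoring problem can be solved without changing visits.

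**Conclusion.** The point holds for time to remission. The definition lacks a reference PCR and a confirming value, and it is met or missed at roughly 12 to 18 tests in a year. If the within-patient log-SD is 0.2 to 0.3, between about a quarter and four fifths of patients with a true fall of 20–40% would be scored as remitters at some visit, depending on the fall and on how fast it develops. At 0.1 the effect is largely confined to falls near 40%.

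Loss of power to detect an MMF effect on this endpoint is plausible and, under the stated assumptions, substantial. The exact loss is illustrative. The documents do not support extending the point to the sample size, and they support it only weakly for the primary endpoint. This is a cheap improvement to a secondary endpoint, not a flaw in the main comparison.

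**What to change.** In section 4.5, for the secondary endpoints only:
- Name the reference PCR: the last value before randomisation, or the mean of the last two where available.
- Date remission, complete or partial, at the first of two consecutive qualifying PCRs at scheduled visits.
- State whether the degree of remission is scored as ever reached or as status at 12 months.

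Visit frequency and treatment decisions stay with the clinic. The wording should be settled before the 12-month response analysis, so that the rule is not chosen with the data in view.

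Confirmation is the essential part. At CV 20%, averaging three reference values while still accepting a single follow-up value leaves 21%, 51% and 85% of patients with a true 20%, 30% and 40% fall scored as remitters.

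The cost is a few sentences, and the follow-up samples are already planned. The reported remission rate will be lower, by an amount that depends on how many patients have modest falls. Patients whose next visit is later will be confirmed later. Near a 40% fall, false remissions drop to about 43–55% at log-SD 0.2 to 0.3 and are not removed. Genuine responders are barely affected: with a true 70% fall present throughout, about 99% or more are still captured at these SDs.

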4.4 Withdrawal and treatment failure

Patients can be withdrawn at patient or physician request. The reason for withdrawal will be recorded in the patients records.

Patients not achieving remission at 1 year will be withdrawn from the trial and alternative treatments considered. They will remain under follow up in the clinic as is current standard practice.

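### Patients not in remission at 1 year leave the trial and nothing brings their later renal data into the eGFR endpoint; the relapse test is conditional on remission with no all-randomised comparison beside it

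*Combined protocol and SAP*

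**What the plan says.** **Withdrawal and follow-up.** Section 4.2 withdraws non-remitters: "Patients not obtaining complete or partial remission after 1 year will be withdrawn from the trial and alternative therapies considered". Section 4.4 says the same and adds: "They will remain under follow up in the clinic as is current standard practice". Section 4.2 also states in general terms: "Patients will be followed for at least 3 years", and section 4.7 plans 36 months of follow-up. Section 4.3 describes what is collected, in a schedule written for trial patients: "At each clinic visit blood samples will be sent for full blood count, biochemical profile, drug level monitoring and selective proteinuria". Urine PCR is also taken at each visit.

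**Renal endpoint.** Section 4.5 lists as secondary: "The rate of decline of renal function measured by the MDRD equation for glomerular filtration rate". It names no analysis population and no time window. Section 4.6 gives no analysis for it. Section 2 makes preservation of renal function one of the trial's aims.

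**Primary endpoint.** The primary question is relapse of nephrotic syndrome once tacrolimus is withdrawn. Section 4.5 says: "This will be initially measured at 6 months post withdrawal of tacrolimus therapy". Withdrawal starts only after sustained remission: "When patients have been in remission for 12 months on treatment the tacrolimus will be withdrawn over 6 months". Section 4.7 times the primary analysis by patients with a year of remission who have then been off tacrolimus for 6 months. Section 3 expects MMF to improve initial response as well as reduce relapse. Section 4.6 names a one-sided log-rank test, defines no analysis population and plans no comparison of all randomised patients.

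**The concern.** There are two separate problems.

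First, persistent proteinuria is the reason a patient is withdrawn at 1 year. If eGFR collection for the trial stops there, the missing data are concentrated in the patients whose renal course matters most to the renal aim. If MMF improves remission, as section 3 expects, the loss is also unequal between arms, and a comparison of eGFR slopes may then be biased. The size of that bias depends on the model and on remission rates, neither of which the documents give, so no size is claimed.

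Second, the patients who reach tacrolimus withdrawal are selected by their response to the randomised treatment. Patients who remit only with MMF added may be more or less prone to relapse than those who remit on tacrolimus alone. A log-rank comparison among remitters therefore mixes any effect of MMF on relapse with differences in who remitted. Keeping non-remitters in follow-up does not remove this. It needs a second analysis that starts from randomisation.

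**Working it through.** **Inputs from the documents.** 32 patients, 16 per arm (section 4); withdrawal of non-remitters at 12 months (4.2, 4.4); 36 months of follow-up (4.7); relapse-free survival 50% against 95%, one-sided alpha 0.05, power 80%, drop-out 1% (4.6). No remission rate is given; the summary says only that tacrolimus works in most patients. Every remission rate below is assumed.

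**1. Follow-up lost for eGFR.** Assume a 36-month window and no use of clinic data after withdrawal. The share lost per arm is 16 × (1 − remission) × 24 / (16 × 36).

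| Assumed remission | Patient-months lost of 576 | Share |
|---|---|---|
| 60% | 153.6 | 26.7% |
| 75% | 96.0 | 16.7% |
| 85% | 57.6 | 10.0% |

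**2. Selection in the relapse comparison.** Assume remission of 60% on tacrolimus and 85% on the combination, so 25% remit only with MMF. Let 50% relapse among those who would remit on either regimen, and a share r among those who remit only with MMF. With no true MMF effect on relapse, the combination arm's relapse share is (0.60 × 0.5 + 0.25r)/0.85.

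- r = 0.8: 0.588, apparent HR ln(1 − 0.588)/ln(0.5) = 1.28.
- r = 0.2: 0.412, apparent HR 0.77.

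Selection alone can therefore push the result either way. Applying the planned HR, ln(0.95)/ln(0.5) = 0.074, within each group gives relapse of 6.8% (r = 0.8) or 4.0% (r = 0.2) against 50%, so an effect of the planned size remains plain.

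**3. Timing of a fixed all-randomised assessment.** Remission by month 12 at the latest, then 12 months in remission, 6 months of withdrawal and 6 months off drug: 12 + 12 + 6 + 6 = 36 months. The earliest case is 0 + 12 + 6 + 6 = 24 months.

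**4. Power of that comparison.** Success is remission × relapse-free share. Control: 0.75 × 0.50 = 0.375. Combination: 0.75 × 0.95 = 0.7125, or 0.90 × 0.95 = 0.855. Fisher's test, 16 against 16, alpha 0.05:

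| Remission, control v combination | One-sided | Two-sided |
|---|---|---|
| 75% v 75% | 49% | 35% |
| 75% v 90% | 83% | 71% |

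**5. Sample size (minor note).** The plan's figure reproduces. Freedman events = (1.645 + 0.842)² × (1.074/0.926)² = 8.32. The mean event probability is (0.50 + 0.05)/2 = 0.275, so N = 30.2, and 30.2/0.99 = 30.5, rounded up to 16 per arm = 32. This assumes that essentially all randomised patients enter the relapse comparison. Freedman power, Φ(√(0.275n) × 0.926/1.074 − 1.645), is 82% at n = 32, 78% at 28.8 (90% remission), 72% at 24 (75%) and 63% at 19.2 (60%). A simulated one-sided log-rank test (exponential times, everyone followed to a fixed time) gives about 94% at 16 v 16, 86–87% at 12 v 12, 87% at 10 v 14, 83% at 11 v 11 and 79% at 10 v 9.

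**The case against.** **The data will exist anyway.** The trial runs through one clinic, and non-remitters stay in it. Their creatinine and PCR would probably be on file. This stands as far as it goes, and a reader should not infer that the data are certain to be lost. But being seen in routine care is not being in the trial, and nothing says the results will be used.

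**Three years of follow-up contradicts withdrawal at 1 year.** A reader might infer this, but a general statement and an explicit rule for one group read naturally as a rule and its exception. The issue is what following the rule does to the renal endpoint.

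**Conditioning on remission is inherent in the question.** Relapse on stopping a drug can occur only in patients who responded and stopped, and section 2 asks exactly that. The question is legitimate, and section 4.7's sentence gives analysis timing and is not written as a population definition. Initial response has its own endpoints at 12 months, which are not affected. But those endpoints do not measure relapse, so no planned analysis covers the whole course from randomisation.

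**The trial is underpowered.** This stronger reading is tempting because nothing in N = 32 allows for non-remission. It is not supported. Freedman's formula is conservative for an effect this large, and simulated power stays near or above 80% until about a third of patients are lost.

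**Conclusion.** The point holds in two parts and is worth fixing because the remedy is cheap. Followed as written, the withdrawal rule cuts eGFR data off at 1 year in patients with persistent proteinuria: 24 of 36 months each, or 26.7% against 10.0% of planned follow-up by arm at 60% against 85% remission. Those figures rest on three assumptions: the remission rates, a 36-month eGFR window, and no use of later clinic data. The relapse comparison is between groups formed after randomisation. A reader might infer that it is biased in favour of MMF, but the documents fix neither direction nor size; the illustrations run from HR 0.77 to 1.28 with no true effect. The planned effect would survive in those scenarios; a modest or null result would be hard to read. The missing allowance for non-remission is a note only, and the stated 80% power is not shown to be wrong.

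**What to change.** (a) In 4.2 and 4.4, state that non-remitters leave the trial regimen but stay in trial data collection to 36 months, with eGFR and PCR taken from their existing clinic visits (for example at months 18, 24, 30 and 36). Treatment decisions are unchanged.

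(b) In 4.5 and 4.6, analyse rate of eGFR decline in all randomised patients with a mixed model over a stated window, and record therapies started after 1 year.

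(c) Keep the one-sided log-rank test as primary and label it conditional on remission. Add a supporting comparison of all randomised patients at one fixed time, 36 months from randomisation: in remission, off tacrolimus and relapse-free, with non-remission counted as failure.

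**Cost.** Four data points in each non-remitter is 32 × 0.10 × 4 = 12.8 to 32 × 0.40 × 4 = 51.2, about 13 to 51 records at 90% to 60% remission. Later eGFR will reflect other therapies, and the slope comparison is probably imprecise at 16 per arm. The composite can favour MMF through remission alone, and its power is modest. At a fixed 36 months, time off tacrolimus ranges from 6 months (remission at month 12) to nearly 18 (36 − 12 − 6, for very early remission). As a supporting analysis it takes no power from the primary test.

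### The primary endpoint refers only to tacrolimus withdrawal, although section 4.2 stops MMF first; a relapse between the two steps is not clearly counted, and Appendix 1 does not state the order

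*Combined protocol and SAP*

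**What the plan says.** - **Section 4.2, trigger and taper:** "When patients have been in remission for 12 months on treatment the tacrolimus will be withdrawn over 6 months".
- **Section 4.2, combination arm:** "Those on MMF and tacrolimus will then have their MMF stopped prior to tacrolimus withdrawal over 6 months". No interval between the MMF stop and the start of the taper is given.
- **Appendix 1:** the line "Withdrawal of tacrolimus over 6 months Withdrawal of tacrolimus over 6 months" gives the same taper for both arms. The instruction to stop MMF is printed below it, with nothing to say whether it comes before, during or after the taper.
- **Section 4.5, primary endpoint:** "Efficacy of MMF in preventing relapse of nephrotic syndrome on withdrawal of tacrolimus therapy", with the timing "This will be initially measured at 6 months post withdrawal of tacrolimus therapy". Section 4.7 also times the primary analysis from the end of tacrolimus.
- **Section 2, aim:** "We wish to investigate whether the addition of MMF will allow the subsequent withdrawal of tacrolimus without precipitating relapse".
- **Section 3, hypothesis:** when MMF is added, "it is likely to improve the initial response to treatment and reduce the risk of relapse on stopping therapy". The rationale in section 1.2 hopes that the combination "will allow the eventual withdrawal of immunosuppressive agents without relapse".
- **Section 4.6:** the main outcome is time to relapse, compared by a one-sided log rank test. No time origin is stated.

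**The concern.** The endpoint names MMF as the agent that prevents relapse and tacrolimus withdrawal as the challenge. Under the section 4.2 order, MMF has already gone when that challenge begins. A result reported in the endpoint's words would invite the conclusion that MMF protects patients while tacrolimus is withdrawn, which the trial would not have tested.

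There is also a question of which relapses count. The combination arm has two withdrawal steps and the monotherapy arm has one. If the clock starts with the tacrolimus taper, a relapse that follows the first step in the combination arm is not a primary event, and the monotherapy arm has no matching step. The planned combination-arm relapse rate is so low that one such event would matter.

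**Working it through.** **1. The plan's own figure.** Inputs from section 4.6: relapse-free rates of 50% and 95%, one-sided alpha 0.05, power 80%, drop-out 1%.
- Hazard ratio: ln(0.95)/ln(0.50) = 0.074.
- Events (Freedman): (1.645 + 0.842)² × [(1 + 0.074)/(1 − 0.074)]² = 8.32.
- Mean event probability: (0.50 + 0.05)/2 = 0.275.
- Patients: 8.32/0.275 = 30.2; allowing for drop-out, 30.2/0.99 = 30.5. This is consistent with 32 in two arms of 16.

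The sample size therefore reproduces. The order of stopping the drugs is not an input to it.

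**2. Time off MMF at the primary time point.** Let g ≥ 0 be the unstated interval, in months, from MMF stop to taper start.
- Section 4.2 order: g + 6 (taper) + 6 (after tacrolimus) = 12 + g, so at least 12 months.
- Appendix 1, read as both actions belonging to one withdrawal step that opens with the MMF stop: 6 + 6 = 12 months.
- Appendix 1, read as MMF stopped at or after the end of the taper: at most 6 months.

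The chart does not settle which reading is meant.

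**3. Which relapses the endpoint covers, under the section 4.2 order.**

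| Period | Monotherapy arm | Combination arm | Covered by the endpoint wording? |
|---|---|---|---|
| MMF stop to taper start (g) | no such step | MMF stopped, tacrolimus continues | not clearly |
| Taper (6 months) | tacrolimus being reduced | same, MMF already off | yes |
| 6 months after tacrolimus | no study drug | no study drug | yes |

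The first row is the only period in which a relapse can follow drug withdrawal in one arm alone.

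**4. Size of one such event.**
- As a share of the randomised arm: 1/16 = 6.25%.
- As a share of those who reach withdrawal: 1/m with m ≤ 16, so 6.25% or more. Sections 4.2 and 4.4 withdraw patients without remission at 1 year, so m may be below 16.
- Planned combination-arm relapses: 5% × 16 = 0.8.
- Against the planned difference of 95 − 50 = 45 percentage points: 6.25/45 = 14%.

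**5. Power if counting these relapses lowers the combination-arm rate.** The alternative rates are assumptions; the control rate is held at 50%, with 16 per arm and no drop-out. With p the combination-arm relapse-free rate, h = ln(p)/ln(0.50) and D = 16 × (0.50 + 1 − p), power = Φ(√D × (1 − h)/(1 + h) − 1.645).
- p = 0.95: D = 8.8, h = 0.074, power 82%.
- p = 0.90: D = 9.6, h = 0.152, power 74%.
- p = 0.85: D = 10.4, h = 0.234, power 64%.

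**The case against.** The strongest reply is that section 4.2 does what the protocol set out to do. The hypothesis concerns relapse once therapy stops, and the rationale concerns withdrawing both agents. A lasting benefit of earlier combined treatment is a legitimate target, and the aim in section 2 never says that MMF continues. This stands. It means that the endpoint wording, rather than the idea behind the trial, needs correcting.

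Three stronger readings are tempting, and the documents do not support them.
- **That the protocol gives two opposite orders, and so describes two different experiments.** Only section 4.2 states an order. Appendix 1 is a chart whose layout is lost in the text available here, and its MMF line carries no word of sequence; it may simply list both actions of the withdrawal step. Print order is a poor guide, since section 4.2 itself mentions the taper first and yet has MMF stopped before it. Nothing says that MMF continues through the taper.
- **That different sites would follow different orders.** Section 4 describes a single centre. Differing practice between clinicians in one clinic is conceivable, but nothing shows it.
- **That the primary comparison is biased towards MMF.** The interval g could be close to zero. Because section 4.6 gives no time origin, a relapse before the taper is not clearly excluded either. The direction is known only if such relapses are left out.

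**Conclusion.** The point holds as a mismatch between treatment sequence, endpoint wording and the events counted. Under section 4.2, MMF is absent for the whole period that the endpoint describes, so the worded conclusion is broader than the design supports. A relapse between the MMF stop and the taper has no clear status, and omitting it would favour MMF. Section 4.2 and Appendix 1 are not clearly aligned; a direct contradiction between them is not shown.

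The size cannot be estimated, because neither the interval nor the risk of relapse within it is given. One event would be 6.25% of 16 patients, or more of those who reach withdrawal, where 0.8 relapses are planned. All of this assumes that the section 4.2 order is the one followed. The sample size is not in question.

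**What to change.** 1. State one sequence in both section 4.2 and Appendix 1, with the interval between the two steps. The choice of order is the sponsor's.
2. If the section 4.2 order stands, reword the primary endpoint as relapse during and after withdrawal of study immunosuppression, by randomised initial regimen.
3. In section 4.6, define a time origin common to both arms and no later than the first stop or reduction of any study drug. The date on which the 12-month remission criterion is met would serve. A relapse before the taper is then a primary event. Interpretation should allow for the interval, since on a common clock a gap puts the taper later in the combination arm.
4. Limit the conclusion to the effect of the initial regimen on relapse once therapy is withdrawn.

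The cost is a wording amendment to sections 4.2, 4.5, 4.6 and 4.7 and Appendix 1, with no extra patients or visits. The combination arm may gain an event. If that reflected a true relapse-free rate below 95%, power would fall as shown in the working.
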